4.9 INTERIM ANALYSES

No interim analysis is planned.

For Study A, a primary database lock will be performed when all randomized participants in this study have completed their 24-week treatment phase. Analysis will be based on all data collected up to the database cut-off date and will be considered as the final analyses in the Study A CSR.

The database will be updated at the end of the study for all participants to include the post-treatment follow-up information and updates for the events previously ongoing at the time of the primary lock. Additional data between this database lock and last participant completing last visit will be summarized in a CSR addendum.

5 SUPPORTING DOCUMENTATION

5.1 APPENDIX 1 LIST OF ABBREVIATIONS

| | |
|-------------|---|
| AAS7: | angioedema activity score over 7 days |
| ADA: | anti-drug antibody |
| AE: | adverse event |
| AESIs: | adverse events of special interest |
| ALT: | alanine aminotransferase |
| ANCOVA: | analysis of covariance, analysis of covariance |
| AST: | aspartate aminotransferase |
| ATC: | anatomic category |
| CDG: | customized drug grouping |
| CDLQI: | children's dermatology life quality index |
| CI: | confidence interval, confidence interval |
| CLcr: | creatinine clearance |
| CMH: | Cochran-Mantel Haenszel |
| CSU: | chronic spontaneous urticaria |
| CU-Q2oL: | chronic urticaria quality of life questionnaire |
| DLQI: | dermatology life quality index |
| DNA: | deoxyribonucleic acid |
| ECG: | electrocardiogram |
| eCRF: | electronic case report form |
| EMA: | European Medicines Agency |
| EOT: | end of treatment |
| EQ-5D-5L: | 5-level EuroQol 5-dimensional questionnaire |
| EQ-5D-Y 5L: | EuroQol 5-dimensional questionnaire youth |
| EU: | European Union |
| FDA: | Food and Drug Administration |
| H1-AH: | H1-antihistamines |
| HBc Ab: | hepatitis B core antibody |
| HBs Ab: | hepatitis B surface antibody |
| HBs Ag: | hepatitis B surface antigen |
| HBV: | hepatitis B virus |
| HCV Ab: | hepatitis C virus antibodies |
| HLGT: | high level group term |
| HLT: | high level term |
| HRQoL: | health-related quality-of-life |
| HSS7: | weekly hives severity score |
| IMP: | investigational medicinal product |
| IRT: | interactive response technology |
| ISS7: | weekly itch severity score |
| ITT: | intent-to-treat |
| LLT: | lower-level term |

| | |
|---------|--|
| LS: | least squares, least squares |
| MCID: | minimal clinically important difference |
| MCMC: | Markov Chain Monte Carlo |
| MedDRA: | medical dictionary for regulatory activities |
| MI: | multiple imputation |
| MID: | minimal important difference |
| OCS: | oral corticosteroids |
| PCSA: | potentially clinically significant abnormality |
| PGIC: | patient global impression of change |
| PGIS: | patient global impression of severity |
| PK: | pharmacokinetic |
| PT: | preferred term |
| RNA: | ribonucleic acid |
| SAE: | serious adverse event |
| SAP: | statistical analysis plan, statistical analysis plan |
| SD: | standard deviation |
| SDG: | standardized drug grouping |
| SDGs: | Standardized drug groupings |
| SMQ: | standardized MedDRA query |
| SOC: | system organ class |
| TEAE: | treatment-emergent adverse event |
| UAS7: | weekly urticaria activity score |
| UCT: | urticaria control test |
| ULN: | upper limit of normal |
| WHO-DD: | World Health Organization-Drug Dictionary |
| WOCF: | worst-observation carried forward |

5.2 APPENDIX 2 CHANGES TO PROTOCOL-PLANNED ANALYSES

This Statistical Analysis Plan (SAP) for study EFC16461 is based on the protocol dated 29 April 2021 (amended protocol 4). This section summarizes major statistical changes in the protocol amendment(s).

The primary purpose of Amended protocol 2 was to increase the sample size of Study A (omalizumab naïve population) based on recommendation from Food and Drug Administration (FDA) to power the studies using conservative assumptions with regard to treatment effect and variability and to include children aged ≥ 6 to <12 years, and to switch the primary and the key secondary endpoints to establish the UAS7 as the primary endpoint for EU and EU reference countries based on recommendations from European Medicines Agency (EMA).

Table 9 - Major statistical changes in protocol amendment(s)

| Amendment Number | Date Approved | Rationale | Description of statistical changes |
|-------------------------|----------------------|---|---|
| 2 | 30-Apr-2020 | 
FDA request to power the study using conservative assumptions with regards to treatment effect and variability and include children
 
EMA request to change the primary and key secondary endpoints for EU and EU reference countries
 
Efficacy analysis was modified to include covariates
 | 
Sample size was increased in Study A from 80 to 130 with a more conservative effect size and up to 5% of participants will now be children. Power increased from 90% to 96%.
 
For EU and EU reference countries only, primary endpoint is now change from baseline in UAS7 at Week 24 and key secondary endpoint is change from baseline in ISS7 at Week 24.
 
Presence of angioedema at baseline was added as a covariate to the primary endpoint analysis and by baseline disease severity, and presence of angioedema at baseline were added to Cochran-Mantel Haenszel (CMH) test. The corresponding baseline value and presence of angioedema at baseline was added as covariates for time-to-event endpoints.
 |

5.3 APPENDIX 3 DEMOGRAPHICS AND BASELINE CHARACTERISTICS, PRIOR OR CONCOMITANT MEDICATIONS

Demographics, baseline characteristics, medical surgical history

The following demographics and baseline characteristics, medical and surgical history and disease characteristics at baseline will be summarized using descriptive statistics in the randomized population.

Demographic variables are

- Age in years (quantitative and qualitative variable: <12, 12- <18, 18- <40, 40 - <65, 65 - <75 and \geq 75 years),
- Gender (Male, Female),
- Race (White, Black or African American, Asian, American Indian or Alaska Native, Native Hawaiian or other Pacific Island, unknown),
- Ethnicity (Hispanic or Latino, Not Hispanic or Latino, Unknown)
- Region (**Asia**: China, Japan; **Latin America**: Argentina; **Western Countries**: Canada, USA, France, Germany, Spain, United Kingdom, **East Europe**: Hungary, Russia)
- Territory (**North America**: Canada, USA; **European Union and UK**: France, Germany, Spain, United Kingdom, Hungary; **Rest of World**: China, Japan, Argentina, Russia)
- Weight in kg (quantitative and qualitative variable: <60, \geq 60 kg)
- BMI in kg/m² (quantitative and qualitative variable: <30, \geq 30 kg/m²)

Baseline safety and efficacy parameters (apart from those listed above) will be presented along with the safety and efficacy summaries.

Medical (or surgical) history includes all the relevant medical (or surgical) history during the lifetime of the participant.

This information will be coded using the version of MedDRA currently in effect at Sanofi at the time of database lock.

Comorbidity will be summarized separately. The following comorbid diseases will be summarized from electronic case report form (eCRF) pages which were filled in by investigators based on participant reporting. Angioedema history will be further summarized under disease characteristics at baseline.

CSU history (Yes, Ongoing condition)

Angioedema (Yes, Ongoing condition)

Atopic Dermatitis (Yes, Ongoing condition)

Allergic rhinitis (Yes, Ongoing condition)

Allergic Conjunctivitis (Yes, Ongoing condition)

Asthma (Yes, Ongoing condition)

Food allergy (Yes, Ongoing condition)

Chronic Rhinosinusitis (Yes, Ongoing condition)

Nasal Polyps (Yes, Ongoing condition)

Eosinophilic Esophagitis (Yes, Ongoing condition)

Disease characteristics at baseline

The following baseline disease characteristics will be summarized by intervention group:

- Age at onset of CSU (years)
- Time since first diagnosis of CSU (years) to be derived as
(Year of randomization – Year of first diagnosis of CSU) + (month of randomization-month of first diagnosis of CSU)/12
- Presence of angioedema at baseline
 - Number of episodes in past 6 months
 - Time since last episode (months)
- Baseline ISS7 score (quantitative and qualitative variable: <13, ≥ 13)
- Baseline UAS7 score (quantitative and qualitative variable: <28, ≥ 28)

- Baseline weekly hives severity score (HSS7)
- Baseline angioedema activity score over 7 days (AAS7) for participants with angioedema
- Baseline urticaria control test (UCT)
- Baseline Dermatology Life Quality Index (DLQI)/Children's Dermatology Life Quality Index (CDLQI)
- Baseline Patient Global Impression of Severity (PGIS)
- Frequency of alcohol drinking in the past 12 months (never, occasional, at least monthly, at least weekly, at least daily) and number of drinks on a typical day (1 or 2, >2)
- Baseline IgE (quantitative and qualitative variable: <100 vs ≥100)
- Baseline H1-AH dose (1-fold, 2-3-fold, 4-fold)

Prior or concomitant medications

All medications taken within 1 month before screening and until the end of the study, including all prior medications taken for CSU are to be reported in the case report form pages.

All medications will be coded using the World Health Organization-Drug Dictionary (WHO-DD) using the version currently in effect at Sanofi at the time of database lock.

- Prior medications are those the participant used prior to first investigational medicinal product (IMP) injection. Prior medications can be discontinued before first administration or can be ongoing during treatment phase.
- Concomitant medications are any interventions received by the participant concomitantly to the IMP, from first administration of IMP to last IMP intake + 98 days.
- Post-treatment medications are those the participant took in the period running from the end of the concomitant medications period up to the end of the study.
- A given medication can be classified as a prior medication and/or as a concomitant medication and/or as post-treatment medication. If it cannot be determined whether a given medication was taken prior or concomitantly or post, it will be considered as prior, concomitant, and post-treatment medication.

The prior and concomitant medications will be summarized for the randomized population

Medications will be summarized by intervention group according to the WHO-DD dictionary, considering the first digit of the anatomic category (ATC) class (anatomic category) and the first 3 digits of the ATC class (therapeutic category). All ATC codes corresponding to a medication will be summarized, and participants will be counted once in each ATC category (anatomic or therapeutic) linked to the medication. Therefore, participants may be counted several times for the same medication.

Prior medications will be summarized separating for those taken for CSU versus other reasons. The tables for prior medications will be sorted by decreasing frequency of ATC followed by all other therapeutic classes based on the overall incidence across intervention groups. In case of equal frequency regarding ATCs (anatomic or therapeutic categories), alphabetical order will be used.

Concomitant medication received during first IMP to last IMP +14 days (+28 days for children <30 kg) and concomitant medication received during first IMP to last IMP +98 days will be summarized separately. The tables for concomitant medications will be sorted by decreasing frequency of ATC followed by all other therapeutic classes based on the incidence in the dupilumab group. In case of equal frequency regarding ATCs (anatomic or therapeutic categories), alphabetical order will be used.

Medications will also be summarized by generic name sorted by decreasing frequency based on the incidence in the dupilumab group.

Rescue medications

The following rescue medications may be used:

- Additional doses of H1-AH up to 4-fold the recommended dose (2-fold in Japan)
- Short course of OCS

The use of rescue medications should be delayed, if possible, for at least 8 weeks following the initiation of IMP. The following specific medications will be summarized:

- Rescue medications taken during the study will be summarized separately overall and by type (additional doses of H1-AH medications, OCS therapy).
- The total number of days rescue medication was taken by type will be summarized.

5.4 APPENDIX 4 DATA HANDLING CONVENTIONS

Demographic formulas

Age of onset of CSU is calculated as:

$$\text{Year of CSU diagnosis} - \text{Year of birth}$$

BMI is calculated as:

$$\text{Weight in kg} / (\text{height}^2 \text{ in meters})$$

Renal function formulas

For adults, creatinine clearance (CLcr) value will be derived using the equation of Cockcroft and Gault:

$$\text{CLcr (ml/min)} = (140 - \text{age}) \times \text{weight (kg)} \times (1 - 0.15 \times \text{sex (0-M, 1-F)}) / (0.814 \times \text{creatinine} (\mu\text{mol/L}))$$

For participants <18 years old, CLcr value will be derived using the equation of GFR Bedside Schwartz

$$\text{GFR (mL/min/1.73 m}^2\text{)} = k \times \text{height (cm)} / \text{sCr (mg/dL)}$$

where the coefficient $k = 0.55$ for children <12; $k = 0.65$ for male adolescent participants or $k = 0.55$ for female adolescent participants

CLcr will be calculated using the last weight measurement on or before the visit of the creatinine measurement and age at the lab sampling day. Here age is calculated as following:

$$\text{Age} = \text{age collected at screening} + \text{integer part of (lab sampling analysis day / 365.25)}$$

Data handling conventions for other secondary endpoints

For the UCT, in case of missing items the score for that participant will be left missing.

- i. For the DLQI, handing of missing items is as follows: If one question is left unanswered this is scored 0 and the scores are summed and expressed as usual out of a maximum of 30
- ii. If two or more questions are left unanswered the questionnaire is not scored
- iii. If question 7 is answered 'yes' this is scored 3 even if in the same question one of the other boxes is ticked
- iv. If question 7 is answered 'no' or 'not relevant' but then either 'a lot' or 'a little' is ticked this is then scored 2 or 1
- v. If two or more response options are ticked for one question, the response option with the highest score should be recorded

For the CDLQI, handling of missing items is as follows:

- i. If one question is left unanswered this is scored 0 and the scores are summed and expressed as usual out of a maximum of 30
- ii. If two or more questions are left unanswered the questionnaire is not scored
- iii. If two or more response options are ticked for one question, the response option with the highest score should be recorded

For the CU-Q2oL total score, the raw total score will be converted to a 0 to 100 score for analysis using the following formula:

$$\text{CU-Q2oL total score} = (\text{raw score} - 23) * 100 / 92$$

Daily e-diary weekly scores

For the daily efficacy endpoints (ISS, UAS, HSS, and AAS), the time period used to calculate the weekly score at each designated study day is summarized in [Table 10](#). Randomization day is used as the reference day (Day 1).

Table 10 - Weekly efficacy assessments from daily e-diary

| Analysis visit | Day range for calculating weekly score | Target day |
|----------------|--|------------|
| Week 1 | 2-8 | 8 |
| Week 2 | 9-15 | 15 |
| Week 3 | 16-22 | 22 |
| Week 4 | 23-29 | 29 |
| Week 5 | 30-36 | 36 |
| Week 6 | 37-43 | 43 |
| Week 7 | 44-50 | 50 |
| Week 8 | 51-57 | 57 |
| Week 9 | 58-64 | 64 |
| Week 10 | 65-71 | 71 |
| Week 11 | 72-78 | 78 |
| Week 12 | 79-85 | 85 |
| Week 13 | 86-92 | 92 |
| Week 14 | 93-99 | 99 |
| Week 15 | 100-106 | 106 |
| Week 16 | 107-113 | 113 |
| Week 17 | 114-120 | 120 |
| Week 18 | 121-127 | 127 |
| Week 19 | 128-134 | 134 |
| Week 20 | 135-141 | 141 |
| Week 21 | 142-148 | 148 |
| Week 22 | 149-155 | 155 |
| Week 23 | 156-162 | 162 |
| Week 24 | 163-169 | 169 |
| Week 25 | 170-176 | 176 |
| Week 26 | 177-183 | 183 |
| Week 27 | 184-190 | 190 |
| Week 28 | 191-197 | 197 |
| Week 29 | 198-204 | 204 |
| Week 30 | 205-211 | 211 |
| Week 31 | 212-218 | 218 |
| Week 32 | 219-225 | 225 |
| Week 33 | 226-232 | 232 |
| Week 34 | 233-239 | 239 |
| Week 35 | 240-246 | 246 |
| Week 36 | 247-253 | 253 |

Analysis windows for time points

For the safety assessment, the reference date for the derivation of relative days of events or findings will be the date of first IMP administration. Selected safety variables will be summarized by the analysis window defined in [Table 11](#) for the by visit descriptive analysis. All available values from central lab will be assigned to the appropriate visit window. In the event of multiple measurements of the same test in the same window, the one closest to the targeted visit date will be used for the by-visit summary. If they are at the same number of days away from the target day, the latest one will be used. For procedures planned on Visit 2, if it is done on the same date as the first IMP injection but the performance time is missing, it will belong to Visit 2 time window.

Table 11 - Time window for safety endpoints

| Visit | Target Day | Vital signs | Hematology, biochemistry, urinalysis | Hepatitis, HIV serology | Time windows for | | | Physical exam | ECG |
|-------------------|------------|-------------|--------------------------------------|-------------------------|------------------|-----------------|--------|---------------|-----|
| | | | | | Serum pregnancy | Urine pregnancy | | | |
| Visit 1 | -28 to -14 | <-14 | <-14 | 1- | <-14 | | | <-14 | 1- |
| Visit 2 (Week 0) | 1 | -14-1- | -14-1- | | | | -14-1- | -14-1- | |
| Week 4 | 29 | | | | | 1+-42 | | | |
| Week 8 | 57 | | | | | 43-70 | | | |
| Visit 3 (Week 12) | 85 | 1+-126 | 1+-126 | | | 71-98 | | | |
| Week 16 | 113 | | | | | 99-126 | | | |
| Week 20 | 141 | | | | | 127-154 | | | |
| Visit 4 (Week 24) | 169 | 127-210 | 127-210 | | | 155-182 | 1+-210 | 1+ | |
| Week 28 | 197 | | | | | 183-210 | | | |
| Week 32 | 225 | | | | | 211-238 | | | |
| Visit 5 (Week 36) | 253 | >210 | >210 | | | >238 | >210 | | |

1-: up to 1st dose date/time; 1+: after 1st dose date/time;

For the efficacy assessment, the reference date for the derivation of relative days of events or findings will be the randomization day. If a participant receives IMP prior to the randomization by mistake, the reference date of efficacy assessment will be the date of the first IMP administration for that participant. For the primary analyses, all available values of scheduled measurements will be assigned to the appropriate visit window according to [Table 12](#). In the event of multiple measurements of the same test in the same window, the one closest to the targeted visit date will be used for the by-visit summary. If they are at the same number of days away from the target day, the latest one will be used.

Table 12 - Time window for efficacy variables

| Visit | Target Day | Time windows for | | | |
|-------------------|------------|--------------------------|--------|--------|---|
| | | UCT, DLQI/CDLQI, CU-Q2oL | PGIC | PCIS | EQ-5D-5L/EQ-5D-L, missed school/work days |
| Visit 1 | -28 to -14 | | | <-14 | |
| Visit 2 (Week 0) | 1 | <1- | | -14-1- | <1- |
| Visit 3 (Week 12) | 85 | 1+-126 | 1+-126 | 1+-126 | 1+-126 |
| Visit 4 (Week 24) | 169 | 127-210 | >126 | >126 | 127-210 |
| Visit 5 (Week 36) | 253 | >210 | | | >210 |

1: up to randomization and before 1st dose date/time; 1+: after randomization or 1st dose date/time

For the pharmacokinetics/pharmacodynamics variables summary, the reference date for the derivation of relative days of measurements will be the date of first IMP administration if the participant is treated with study intervention, or the randomization date if the participant is not treated. Pharmacokinetics /pharmacodynamics variables will be summarized by the analysis window defined in [Table 13](#) for the by visit descriptive analyses. All available values of measurements will be assigned to the appropriate visit window. In the event of multiple measurements of the same test in the same window, the one closest to the targeted visit date will be used for the by-visit summary. If they are at the same number of days away from the target day, the latest one will be used. For procedures planned on Visit 2, if it is done on the same date as the first IMP injection but the performance time is missing, it will belong to Visit 2 time window.

Table 13 - Time window for pharmacokinetics/pharmacodynamics variables

| Visit | Target Day | Serum dupilumab, ADA, Total IgE | Skin biopsy (substudy) | Basophil activation(substudy) |
|-------------------|------------|---------------------------------|------------------------|-------------------------------|
| Visit 1 | -28 to -14 | | | |
| Visit 2 (Week 0) | 1 | <1- | <1- | <1- |
| Visit 3 (Week 12) | 85 | 1+-126 | | 1+-126 |
| Visit 4 (Week 24) | 169 | 127-210 | >1+ | >126 |
| Visit 5 (Week 36) | 253 | >210 | | |

1-: up to 1st dose date/time or randomization if participant is not treated; 1+: after 1st dose date/time or randomization date if participant is not treated;

Unscheduled visits

Unscheduled visit measurements of laboratory data, vital signs and ECG will be used for computation of baseline, the last on-treatment value, analysis according to PCSAs, and the shift summaries for safety. They will also be included in the by-visit summaries if they are re-allocated to scheduled visits. Unscheduled visit measurements for efficacy data will be included in the by-visit summaries if they are re-allocated to scheduled visits.

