### Methods of assigning patients to treatment group

The randomized intervention kit number list is generated centrally by Sanofi and IMPs (dupilumab 300 mg, dupilumab 200 mg, or their matching placebo) are packaged in accordance with this list. The randomization and intervention allocation are performed centrally by an IRT. The IRT generates the participant randomization list and allocates the intervention number and the corresponding intervention kits to the participants according to it.

Participants will be randomized in a 1:1 ratio treatment arm described in [Table 3](#).

The randomization will be stratified first by age (adults versus adolescents versus children in Study A and Study C and adults versus adolescents in Study B; up to approximately 5% of total sample size for children and approximately 5% of total sample size for adolescents in Study A and Study C; up to approximately 5% of total sample size for adolescents in Study B). In adults, randomization will be stratified further by country (Study A, B and C) and presence of angioedema at baseline (Study C only). In adolescents/children  $\geq 6$  to  $< 12$  years of age, randomization will not be stratified further. In Study A, overall 52% of participants received H1-AH at recommended doses as background therapy, and 45% of participants presented with angioedema at baseline. To maintain consistency between the study population in studies A and C, and reflect the real-life distribution of patients with angioedema and uncontrolled by both standard dose or maximal H1-AH therapy, it is planned that Study C would include not more than

approximately 50% (n=75) of participants having their H1-AH therapy at recommended doses (for more details please see Section 6.1.2), and not less than approximately 30% (n=45) but not more than approximately 45% (n=68) of participants presenting with angioedema at baseline.

It is anticipated that approximately 30%-40% of enrolled participants will have angioedema.

A randomized participant is defined as a participant who has been allocated to a randomized intervention regardless whether the treatment was administered or not (ie, participant registered by the IRT). A participant cannot be randomized more than once in the study.

Investigational medicinal products will be dispensed at the study visits summarized in the Schedule of activities (SoA).

Returned IMP should not be re-dispensed to the participants.

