3 ANALYSIS POPULATIONS

The following populations for analyses are defined:

Table 4 - Populations for analyses

| Population | Description |
|--------------------------|--|
| Screened | All participants who sign the ICF. |
| Randomized | All participants from the screened population who have been allocated to a randomized intervention by IRT regardless of whether the treatment kit was used or not. Participants treated without being randomized will not be considered randomized and will not be included in any efficacy population. |
| Intent-to-treat (ITT) | All randomized participants analyzed according to the intervention group allocated by randomization. |
| Safety | All participants randomly assigned to study intervention and who take at least 1 dose of study intervention. Participants will be analyzed according to the intervention they actually received. Randomized participants for whom it is unclear whether they took the study medication will be included in the safety population as randomized. For participants who accidentally receive a different intervention from that which was planned, the actual intervention allocation for as-treated analysis will be the dupilumab group. The pharmacodynamic (PD) analyses will be performed on the safety population. |
| Pharmacokinetic (PK) | The PK population includes all participants in the safety population with at least one non-missing result for functional dupilumab concentration in serum after first dose of the study intervention. Participants will be analyzed according to the intervention actually received. |
| Anti-drug antibody (ADA) | ADA population includes all participants in the safety population who have at least one non-missing ADA result after first dose of the study intervention. Participants will be analyzed according to the intervention actually received. |

Abbreviations: ADA = antidrug antibody; ICF = Informed consent form, IRT = Interactive response technology; PD = Pharmacodynamic

Participants exposed to study intervention before or without being randomized will not be considered randomized and will not be included in any analysis population. The safety experience of these participants will be reported separately.

Randomized participants for whom it is unclear whether they took the study intervention will be considered as exposed and will be included in the safety population as randomized.

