3 ANALYSIS POPULATIONS

The following populations for analyses are defined:

Table 3 - Populations for analyses

| Population | Description |
|-------------------------|--|
| Screened | All participants who sign the ICF |
| Randomized | All participants from the screened population who have been allocated to a randomized intervention by IRT regardless of whether the treatment kit was used or not. Participants treated without being randomized will not be considered randomized and will not be included in any efficacy population. |
| Intent-to-treat (ITT) | All randomized participants analyzed according to the intervention group allocated by randomization. |
| Safety | All participants randomly assigned to study intervention and who take at least 1 dose of study intervention. Participants will be analyzed according to the intervention they actually received. Randomized participants for whom it is unclear whether they took the study medication will be included in the safety population as randomized. For participants who accidentally receive a different intervention from that which was planned, the actual intervention allocation for as-treated analysis will be the dupilumab group. The pharmacodynamic (PD) analyses will be performed on the safety population. |
| Pharmacokinetic (PK) | The PK population includes all participants in the safety population with at least one non-missing result for functional dupilumab concentration in serum after first dose of the study intervention. Participants will be analyzed according to the intervention actually received. |
| Antidrug antibody (ADA) | ADA population includes all participants in the safety population who have at least one non-missing ADA result after first dose of the study intervention. Participants will be analyzed according to the intervention actually received. |

Abbreviations: ADA = antidrug antibody; ICF = Informed consent form, IRT = Interactive response technology; PD = Pharmacodynamic

Participants exposed to study intervention without being randomized will not be considered randomized and will not be included in any analysis population. The safety experience of these participants will be reported separately.

Randomized participants for whom it is unclear whether they took the study intervention will be considered exposed and will be included in the safety population as randomized.

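### Study A SAP Section 3 removes a participant dosed in error before randomization from every analysis population, against its own Randomized definition, the protocol and SAP 5.4

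*SAP*

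**What the plan says.** **Study A SAP, Section 3.** The Randomized row of Table 4 begins "All participants from the screened population who have been allocated to a randomized intervention by IRT regardless of whether the treatment kit was used or", so kit use has no bearing on membership. It adds one exclusion: "Participants treated without being randomized will not be considered randomized and will not be included in any efficacy population". The ITT row takes all randomized participants by allocated arm, and Section 4.3.2 makes ITT the primary efficacy population. The text below the table is wider: "Participants exposed to study intervention before or without being randomized will not be considered randomized and will not be included in any analysis population". A further sentence provides for separate reporting of their safety findings.

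**Study A SAP, Section 5.4 (analysis windows).** The efficacy reference date is normally the day of randomization, with one exception: "If a participant receives IMP prior to the randomization by mistake, the reference date of efficacy assessment will be the date" of that participant's first dose. The next sentence puts the date to use: "For the primary analyses, all available values of scheduled measurements will be assigned to the appropriate visit window according to" Table 12.

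**Protocol.** Section 6.3: "A randomized participant is defined as a participant who has been allocated to a randomized intervention regardless whether the treatment was administered or not". Table 6 bars from the efficacy populations only participants who were treated and never randomized.

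**Study B and Study C SAPs, Section 3.** The sentence matching the Study A one begins "Participants exposed to study intervention without being randomized will not be considered randomized". It says nothing of exposure before randomization.

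**The concern.** A participant can be dosed by mistake and afterwards be allocated by the IRT; SAP 5.4 foresees exactly this. For that person the Study A SAP gives two answers. Read literally, Section 3 removes an allocated participant from ITT because of something that happened in the conduct of the trial, which is what an ITT definition is meant to prevent. The same sentence takes an exposed participant out of the safety population. With both rules on paper, the choice falls to whoever builds the analysis dataset.

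There is a smaller, related gap. If the participant is kept, the SAP does not say plainly which day anchors the ISS7 and UAS7 weekly scores, or whether the e-diary baseline may contain days after the first dose.

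**Working it through.** **1. One participant, each rule in turn.** Take a participant who signs consent, is dosed in error on day −k, and is allocated by the IRT on day 0.

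- Study A SAP Table 4, Randomized row: allocated by IRT, so in.
- Table 4, exclusion in that row: applies only to those treated and never randomized, so not triggered.
- Table 4, ITT row: in, provided the participant counts as randomized.
- Protocol 6.3 and Table 6: randomized, not excluded.
- SAP 5.4: given an efficacy reference date (day −k). The date has a use only if the participant's efficacy data are analysed.
- Study A SAP Section 3, text below Table 4: not considered randomized; out of every population.
- Study B and C SAPs, Section 3: not excluded.

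Only the text below Table 4 in the Study A SAP gives the answer *out*, and it does so through the words *before or*. Neither the version history nor Appendix 2 of that SAP lists this as a change. The Study A SAP rests on amended protocol 4 and the protocol at hand is amendment 05. The amendment 05 summary of changes attributes the edits to Sections 6.3 and 9.3 to the addition of Study C, its stratification and enrolment limits, and unblinding wording, not to who counts as randomized.

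**2. E-diary anchor and baseline.** The e-diary part of 5.4 (Table 10) sets Day 1 at randomization and states no exception. The exception comes later, in the paragraph leading to Table 12, and that table lists the site-visit questionnaires, not ISS7 or UAS7. Under Table 10 the Week 24 score uses days 163 to 169 from randomization; under the exception it uses days 163 to 169 from first dose, which is k days earlier. Section 4.3.1 takes the baseline from the 7 days before randomization, so k of those 7 days (for k up to 7) fall on or after the first dose. Section 4.1 asks for a pre-dose efficacy baseline unless otherwise specified. The Study B and C SAPs have the same layout.

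**3. Size.** The plan gives no figure on this point and no count of cases.

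- Share of the analysis set: 1/138 = 0.7% (138 randomized, protocol synopsis).
- Shift in the arm difference from adding or removing one participant ≈ residual / participants per arm. The arms are 68 and 70 (protocol Table 1). The SD is 7.5 for ISS7 (pooled from Study A, protocol 9.2). The residual is assumed to be 1 to 2 SD, that is 7.5 to 15 points.
  - 7.5/70 = 0.11 and 15/70 = 0.21; with 68 in the arm, 7.5/68 = 0.11 and 15/68 = 0.22.
  - Against the reported difference of 4.23: 0.11/4.23 = 3% and 0.22/4.23 = 5%.
- Power, for scale. The SAP's 96% reproduces: 65 × 0.85 = 55.25 evaluable per arm gives a t-test power of 0.9541 at effect size 0.7 and 0.9609 at 5/7. Losing one participant from one arm gives 0.9525 and 0.9594.

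**The case against.** The strongest reply is that this concerns two stray words in the SAP of a finished study. Protocol Table 1 reports 68 + 70 = 138 in ITT and the synopsis reports 138 randomized, so nothing suggests that anyone was dropped. The scenario is remote, since kits are allocated through the IRT and site staff give the first injection at Visit 2. The Study C SAP already has the narrower wording. Changing a population rule after the results are known is also more than an edit.

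Most of this stands, as a limit on size. The matching counts are reassuring but not proof: Section 3 would stop counting such a person as randomized, so the totals would agree either way.

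Four stronger readings are tempting, and the documents do not support them:

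- *That 5.4 expressly keeps the participant in ITT.* It sets a reference date; membership is implied. One could let Section 3 govern and treat the 5.4 sentence as redundant. That removes the clash with 5.4 but not the clash with the Randomized row and the protocol.
- *That Section 3 contradicts the ITT row directly.* That row covers all randomized participants, and Section 3 declares these people not randomized. The conflict reaches ITT only through the Randomized row.
- *That safety data would be lost.* Sections 3 and 4.7 both provide for separate reporting.
- *That the e-diary baseline and Day 1 are flatly contradictory, and only in Study A.* The pre-dose rule in 4.1 and the exception in 5.4 cover these points in part, and the same gap recurs in Studies B and C. It calls for clarification.

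**Conclusion.** The conflict over the analysis populations is real and specific to the Study A SAP. Section 3 states a rule that excludes an IRT-allocated participant because of a dosing error, against Table 4's Randomized row, protocol 6.3 and Table 6, and the purpose of SAP 5.4. It is a wrong rule, not a missing detail.

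Its consequence depends on a case having occurred, and none is documented. One case would be 0.7% of the randomized set and move the ISS7 difference by about 0.1 to 0.2 points, if the residual is 1 to 2 SD; that residual is an assumption. A reader might infer that the Study A result is in doubt. The documents do not support that: the reported difference is −4.23 (95% CI −6.63 to −1.84, p = 0.0005), and one participant would not be expected to change the conclusion.

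**What to change.** 1. In Section 3 of the Study A SAP, delete *before or*, as in the Study B and C SAPs. Only participants never randomized are then excluded; everyone allocated by the IRT stays in ITT, and in the safety population if dosed.
2. Because Study A is complete, issue this as a documented correction that states whether any participant was dosed before being randomized and, if so, how that participant was handled.
3. In all three SAPs, state that the first-dose reference date in 5.4 also governs the e-diary weekly windows, and that the e-diary baseline is the 7 days before the earlier of randomization and first dose, in line with 4.1.

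The cost is two words deleted, about a sentence added to each SAP, and a check of dosing dates against randomization dates. No new data are needed. Only if a case is found, and had been left out, would the Study A analyses need rerunning with that participant included.
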